Patients in the monotherapy arms of Part B (i.e., Arm B5 or B6) with confirmed PD may continue on their current study drug and add MEDI4736 at the discretion of the Investigator with notification to the Medical Monitor (and so long as there is active enrolment ongoing in the treatment combination arms for PD-(L)1 naïve patients). In these patients, MEDI4736 will be added to the schedule beginning on Day 1 of the following treatment cycle with AZD9150 and MEDI4736 (i.e., study treatment will be dosed on the same schedule as a patient on a combination therapy arm starting on Day 1 of the following Cycle; see [Table 4](#) for dosing schedule). After addition of MEDI4736, these patients will be followed for safety but censored from the efficacy analysis. When the addition of MEDI4736 (durvalumab) occurs, the first safety reassessment for the combination of treatment in these patients is to take place 45 days after the first administration (of combination treatment) and every 8 weeks thereafter.

All patients will be evaluated according to the study plan (see [Section 5.2](#), [Table 5](#)) and their clinical status classified according to the RECIST guidelines version 1.1 ([Eisenhauer et al 2009](#)) with modifications to account for the unique response kinetics, which have been observed in some patients where responses to immunotherapy may occur after PD is assessed ([Wolchok et al 2009](#)). Specifically, RECIST criteria will be modified so that PD in the absence of clinical deterioration must be confirmed at least 4 weeks after the initial assessment of PD. Study treatment will continue between the initial assessment of progression and the confirmation for progression. Patients may continue to receive study treatment beyond confirmed PD in the absence of clinical deterioration and if the Investigator is of the opinion that the patient continues to receive benefit from treatment.

Following a 7-day lead-in period, each treatment cycle will span 28 days. [Table 4](#) provides an overview of the treatment schedule in the dose-expansion Part B of the study.

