Exposure to IP (i.e., total amount of study drug received) will be listed for all patients by cohort.

Total exposure (date of last dose minus date of first dose + 1) and total time on study (date of discontinuation minus date of first dose + 1) will be summarised by the following: Mean, standard deviation, minimum, maximum, median, and number of observations. In addition, the number and percentage of patients with at least 1 dose interruption/dose delay and at least 1 dose-reduction will be presented separately for the initial period of evaluability defined as 28 days and for any time following this initial period of the study.

Relative dose intensity and percentage intended dose for AZD9150, AZD5069, and MEDI4736 will be derived and summarised by the following: Median, minimum, maximum, 75th percentile, 25th percentile, and number of observations. Relative dose intensity is the percentage of actual dose intensity delivered relative to the intended dose intensity through treatment discontinuation. The entire intended treatment period will be used in the derivation of relative dose intensity.

Safety

No inferential testing will be performed on safety data. Safety data will be summarised using descriptive statistics. At the end of the study, appropriate summaries of all safety data will be produced, as defined below.

AEs will be listed individually by patient and treatment group. For patients who have a dose modification, all AEs (due to drug or otherwise) will be assigned to the associated initial dose combination/treatment dose.

AESIs will also be summarised and listed separately for each compound.

The number of patients experiencing each AE will be summarised by the Medical Dictionary for Regulatory Activities (MedDRA) system organ class, MedDRA preferred term and CTCAE grade. The number and percentage of patients with AEs in different categories (e.g., causally related, CTCAE ≥ 3) will be summarised by dose group, and events in each category will be further summarised by MedDRA system organ class and preferred term, by cohort (as appropriate). SAEs and other significant AEs will be summarised separately if a sufficient number occur.

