### 11.2. TREATMENT EXPOSURE AND DURATION

Exposure is defined as the total amount (in mg) of a study drug component (AZD9150, AZD5069, and MEDI4736) that is received by a patient.

Total treatment duration will be calculated separately for each of the components of study medication. Because the pharmacokinetic profiles of AZ9150, AZD5069, and MEDI4736 differ, the total treatment duration is defined differently for each component of study medication:

For AZD9150:

Total treatment duration (days) = (Date of last dose - date of first dose in Cycle 1) + 7).

For AZD5069:

Total treatment duration (days) = (Date of last dose - date of first dose in Cycle 1) + 1).

For MEDI4736:

Total treatment duration (days) = (Date of last dose - date of first dose in Cycle 1) + 28).

For treme in arm A4:

Total treatment duration (days) = (Date of last dose - date of first dose in Cycle 1) + 28).

Actual treatment duration (days) will be calculated as the total duration of exposure, excluding periods of dose interruption (AZD5069) and planned “no dose” periods for intermittent dosing (AZD9150 and MEDI4736). For AZD5069, periods of dose interruption will be defined as days within the treatment period on which the patient took no tablets of AZD5069. For AZD9150, each planned “no dose” period will be counted as 7 days. For MEDI4736 or treme, each planned “no dose” period will be counted as 28 days.

Duration of therapy (months) is the actual treatment duration for the dose to which the patient was originally assigned or randomized. Duration of therapy will be calculated only for Part B.

The relative dose intensity is the percentage of the actual dose intensity delivered (mg/kg based on ideal body weight) divided by the intended dose intensity (mg/kg based on ideal body weight) through to treatment discontinuation multiplied by 100. The duration of the intended cumulative intended dose is defined as the time up to the earlier of progression (or a censoring event) or the actual last day of dosing.

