## Statistical Analysis Plan

The percent intended dose (PID) is the actual cumulative dose delivered up to progression (or a censoring event) divided by the intended cumulative dose up to progression (or a censoring event). The intended cumulative dose is the total dose that would be delivered, if there were no modifications to dose or schedule.

Time on study will be calculated as follows:

Time on study (days) = (Date of study discontinuation – date of first dose in Cycle 1) + 1

The patient's date of study discontinuation will be taken from the "End of Study" eCRF page. For the combination drugs, only the first dose date of the AZD9150 or AZD5069 component will be used in the calculation of time on study.

The total number of doses received and exposure to each drug component, the total and actual treatment durations, the time on study, the relative dose intensity and PID will be summarized by treatment group using descriptive statistics for continuous variables. Additionally, the summary of relative dose intensity will present 25th and 75th percentiles.

The number and percentage of patients who experience at least 1 dose interruption or dose delay and the number percentage of patients who experience at least 1 dose reduction will be summarized for Cycle 1 and for all subsequent cycles combined.

All AZD9150, AZD5069, and MEDI4736 dosing data recorded on the eCRF will be listed including any treatment modification. Additionally, the derived parameters will be included on the listing.

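### SAP 11.2 gives relative dose intensity two conflicting end points, and on a literal reading patients dosed past progression can score above 100%

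*SAP*

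**What the plan says.** SAP 11.2 takes the actual dose intensity delivered, "divided by the intended dose intensity (mg/kg based on ideal body weight) through to treatment discontinuation multiplied by 100". The next sentence of the same paragraph says that the duration of the intended cumulative dose "is defined as the time up to the earlier of progression (or a censoring event) or the actual last day of dosing". No corresponding limit is stated for the delivered dose.

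The following definition in SAP 11.2, percent intended dose (PID), is matched: "actual cumulative dose delivered up to progression (or a censoring event) divided by the intended cumulative dose up to progression", again with censoring as the alternative end.

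Protocol 8.10 (Exposure) has no progression cut for RDI: "Relative dose intensity is the percentage of actual dose intensity delivered relative to the intended dose intensity through treatment discontinuation". It adds: "The entire intended treatment period will be used in the derivation of relative dose intensity". SAP Section 13, which records changes from the protocol, mentions only the PK, PD and efficacy analysis sets.

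Protocol 4.2.2 makes dosing after first progression part of the design. "PD in the absence of clinical deterioration must be confirmed at least 4 weeks after the initial assessment of PD", and in the meantime "Study treatment will continue between the initial assessment of progression and the confirmation for progression". After that, "Patients may continue to receive study treatment beyond confirmed PD in the absence of clinical deterioration", if the investigator judges that the patient still benefits.

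**The concern.** One paragraph names two end points for the same ratio. For a patient who stops dosing before progression, the delivered dose is the same under either. For a patient dosed past progression they differ, and a programmer following the text could count delivered doses after progression with no intended doses to set against them.

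RDI is meant to show how much of the planned regimen was given. A value inflated by treatment past progression would no longer show that, and a patient with reduced doses could look over-treated. The departure from protocol 8.10 is also unrecorded, so a reader of the study report would not know that the definition had changed.

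**Working it through.** The documents give no RDI figure to reproduce. The check counts doses for an assumed patient who receives every planned dose. Lead-in doses are left out.

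**Inputs**
- First on-treatment tumour assessment: Cycle 2 Day 15 (SAP 8.1), which is Study Day 28 + 15 = 43.
- Earliest confirmation of progression: 4 weeks later (protocol 4.2.2), Day 43 + 28 = 71.
- Progression dated to the initial scan, as protocol 8.9 directs when the investigator was in doubt and repeat scans confirm it.
- AZD9150 weekly, or every 2 weeks in Arm B8; MEDI4736 every 4 weeks; AZD5069 daily.

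**Literal cumulative reading**

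RDI = 100 × (doses delivered to last dose) / (doses intended to progression)

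| Drug | Progression Day 43, last dose Day 71 | Progression Day 85, last dose Day 113 |
|---|---|---|
| AZD9150 weekly | 11/7 = 157% | 17/13 = 131% |
| MEDI4736 | 3/2 = 150% | 5/4 = 125% |
| AZD5069 (days) | 71/43 = 165% | 113/85 = 133% |

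Arm B8 AZD9150, for the first pair of dates, gives 6/4 = 150%. Later progression with the same 4-week gap shrinks the excess: progression on Day 141 and last dose on Day 169 gives 25/21 = 119% for weekly AZD9150. A longer gap enlarges it: progression on Day 43 and last dose on Day 99 gives 15/7 = 214%.

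**Other readings, same compliant patient on weekly AZD9150**
- Both windows through discontinuation: 11/11 = 100%.
- Both windows to progression: 7/7 = 100%.
- Dose per unit time, each part over its own complete dosing intervals: (11/11 weeks) / (7/7 weeks) = 100%.

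**A patient with a dose reduction**

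Assume weekly AZD9150, 3 doses at 3 mg/kg and then 8 at 2 mg/kg, with progression on Day 43 and last dose on Day 71. The pattern is chosen for arithmetic only. Delivered dose is 3 × 3 + 8 × 2 = 25 mg/kg.
- Mismatched windows: 25 / (7 × 3) = 25/21 = 119.0%.
- Both through discontinuation: 25 / (11 × 3) = 25/33 = 75.8%.
- Both to progression: (3 × 3 + 4 × 2) / 21 = 17/21 = 81.0%.

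**Last dosing day against discontinuation**

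Protocol 6.9.1 allows a 21-day recovery period. Take a patient on weekly AZD9150 whose last dose is Day 50, who misses Days 57, 64 and 71, and who then discontinues on Day 71 without progression. With the window ending on the last dosing day, RDI is 8/8 = 100%. With the window through discontinuation, it is 8/11 = 73%. A last-dosing-day end point removes the final hold.

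**The case against.** The strongest reply is that the SAP never states a mismatch. The words on treatment discontinuation follow the intended dose intensity, so they can govern the denominator or the whole ratio; they are not attached to the delivered dose alone. The sentence with the progression cut speaks of an intended cumulative dose, which is PID's term, and it comes just before PID is defined. Dose intensity ordinarily means dose per unit time, and on that reading the compliant patient scores 100%.

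Much of this stands. A reader might infer that RDI certainly sets dose delivered to discontinuation against dose intended to progression, so that everyone treated past progression scores well above 100%. The documents do not support that certainty. The mg/kg unit without a time term and the word cumulative favour the literal reading but do not exclude the others.

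The reply does not clear the text. The sentence sits in the RDI paragraph, where the protocol has its own sentence on the RDI period, and it includes a last-dosing-day limit that PID's definition lacks. If it did belong to PID, it would conflict with PID's denominator for a patient who stops dosing before progression. Either way something needs correcting.

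It is also fair that RDI is not the only view of deliverability. SAP 11.2 separately counts patients with interruptions or delays and with reductions, reports PID, and lists all dosing data. Nor do the documents support an inference that arms with more early progression are distorted more: that depends on how long patients are dosed afterwards, which is not given.

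**Conclusion.** The definition conflicts with itself and departs from protocol 8.10 without being listed in SAP Section 13. Whether reported values are wrong depends on how the text is programmed. On the literal cumulative reading, a compliant patient with progression on Day 43 and last dose on Day 71 scores 150–157% for weekly AZD9150 and MEDI4736, and the assumed reduced-dose patient scores 119% instead of 76% or 81%. With matched windows, or intensity per unit time over complete dosing intervals, the compliant patient scores 100%.

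The figures above 100% also assume that progression is dated to the first scan. If it were dated to confirmation on Day 71, the excess for that patient would vanish. How often patients are dosed past progression is not stated, so the effect on arm medians and quartiles cannot be sized.

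The consequence is limited to a descriptive exposure summary. The primary ORR analysis, DLT and MTD determination, and the futility rules do not use RDI.

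**What to change.** Rewrite the RDI sentences in SAP 11.2 to use one window for both parts: first dose through treatment discontinuation, in line with protocol 8.10. The window should include any treatment past progression and any final dose hold before discontinuation. It should not end at the last dosing day, which is not what protocol 8.10 says and would drop that final hold. State that RDI is the ratio of cumulative delivered to cumulative intended dose over that window.

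Keep the progression cut for PID only, where it already applies to both parts. If the sponsor prefers a progression cut for RDI as well, it should apply to delivered and intended dose alike and be listed in SAP Section 13.

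The cost is a sentence or two in the SAP and a check of the exposure program. No new data are needed.

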## Statistical Analysis Plan

The percent intended dose (PID) is the actual cumulative dose delivered up to progression (or a censoring event) divided by the intended cumulative dose up to progression (or a censoring event). The intended cumulative dose is the total dose that would be delivered, if there were no modifications to dose or schedule.

Time on study will be calculated as follows:

Time on study (days) = (Date of study discontinuation – date of first dose in Cycle 1) + 1

The patient's date of study discontinuation will be taken from the "End of Study" eCRF page. For the combination drugs, only the first dose date of the AZD9150 or AZD5069 component will be used in the calculation of time on study.

The total number of doses received and exposure to each drug component, the total and actual treatment durations, the time on study, the relative dose intensity and PID will be summarized by treatment group using descriptive statistics for continuous variables. Additionally, the summary of relative dose intensity will present 25th and 75th percentiles.

The number and percentage of patients who experience at least 1 dose interruption or dose delay and the number percentage of patients who experience at least 1 dose reduction will be summarized for Cycle 1 and for all subsequent cycles combined.

All AZD9150, AZD5069, and MEDI4736 dosing data recorded on the eCRF will be listed including any treatment modification. Additionally, the derived parameters will be included on the listing.

### 11.3. ADVERSE EVENTS

Adverse events will be collected throughout the study, from informed consent until the end of the follow-up period. All adverse events that occur after administration of the first dose of study drug or that are present at baseline but worsen in intensity after the first dose of study drug will be summarized. All adverse events will be listed.

Adverse events will be summarized by the SOC and PT based on the MedDRA dictionary version 17.1 or later.

The grading scales found in the current CTCAE version 4.03 (14 June 2010) will be utilized for all AEs with an assigned CTCAE grading. For those AEs without assigned CTCAE grades, the recommendation in the CTCAE criteria that converts mild, moderate, and severe events into CTCAE grades will be used.

## Statistical Analysis Plan

For summaries of AEs by SOC and PT, a patient will be counted once at the SOC level and once at each PT within the SOC level. For summaries by SOC, PT, and maximum intensity, a patient will be counted once at the highest intensity level for which the event occurred at the SOC level and the highest intensity level for each unique PT within that SOC level. Therefore, patients may only contribute once to each PT and once to each SOC level.

The summaries presenting frequency of AEs by SOC and PT will be ordered by overall descending frequency of SOC and then, within an SOC, by overall descending frequency of PT.

During the evaluation of the AE data, an INC medically qualified expert will review the list of AEs that were not reported as SAEs and AEs leading to discontinuation of investigational product. Based on the expert's judgment, AEs of particular clinical importance may, after consultation with the Global Safety Physician, be considered other significant AEs (OAEs) and reported as such in the CSR.

The following AE tables will be provided:

- An overall summary of the number and percentage of patients reporting AEs, treatment-related AEs, serious AEs, < Grade 3 or  $\geq$  Grade 3 AEs, AEs considered to be DLTs (see Protocol Section 5.3.2. for definition of DLTs), AEs leading to dose withdrawn, and fatal AEs.
- AEs by SOC and PT
- Most common AEs (i.e., frequency  $\geq$  5%) by PT
- Serious AEs, by SOC and PT
- DLTs
- Study-treatment-related AEs, by SOC and PPT
- Causality Related AEs by CTCAE Grade
- AEs by CTCAE Grade, by SOC and PT
- AEs leading to death, by SOC and PT
- AEs < grade 3 or  $\geq$  grade 3, by SOC and PT

## Statistical Analysis Plan

- AEs leading to study withdrawal, by SOC and PT
- AEs leading to withdrawal of study medication, by SOC and PT
- AEs leading to dose reduction
- Other significant AEs (OAEs), by SOC and PT
- AEs from the start of monotherapy up to the beginning of combination therapy, overall and by SOC and PT
- Bleeding or hemorrhage AEs by SOC and PT.

For analysis purposes, only the following TEAEs or treatment-emergent SAEs will be summarized in the summary tables.

1. For monotherapy arms (AZD9150 or AZD5069 with no MEDI4736), TEAEs from the first dose date of the study drug up to 30 days after the last dose date. Similarly, treatment-emergent SAEs from the first dose date of the study drug up to 35 days after the last dose date. [Note: replace AZD9150 and MEDI4736 with actual names if applying that globally]
2. For combination therapy arms (AZD9150 or AZD5069 with MEDI4736), use both TEAEs and treatment-emergent SAEs from the first dose date of the study drug up to 90 days after the last dose date of MEDI4736.

For patients who have a dose modification, all AEs (due to drug or otherwise) will be assigned to the initial dose group.

Additional listings will be provided for AEs marked as DLTs. TEAEs will be flagged in the listings. Adverse events that occurred during the monotherapy cycle will also be flagged.

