- j For women of childbearing potential, defined as those who are not surgically sterile (i.e., bilateral tubal ligation, bilateral oophorectomy, or complete hysterectomy) or postmenopausal (defined as 12 months with no menses without an alternative medical cause): A blood sample to determine serum β hCG is required at screening; this sample will be analysed at the central laboratory for the study. Additionally, urine samples for a urine-based pregnancy test will be collected before dosing on Day -7 of the lead-in, before dosing on Day 1 of each cycle, and at the EOT visit. Urine-based pregnancy tests will be performed at the study centres.
- k Tumor assessments to be performed at screening, on Day 15 of Cycle 2 (i.e., at the beginning of Week 7), at the beginning of each subsequent even-numbered cycle, and at the EOT visit. Patients who are on study treatment for more than 24 months may have the frequency of tumor assessment reduced to every 12 to 16 weeks at the discretion of the Investigator. Patients who discontinue treatment for reasons other than PD will continue to undergo tumor assessments every 2 months (\pm 7 days) until PD is noted. To facilitate scheduling of tumor assessments, a window of \pm 7 days is allowed. For the additional 48 patients to be enrolled in first-line in Arms B7 and B8, a central imaging read will be done in addition to the local site RECIST evaluation. See Section 5.3.1 for additional details.

- ^l The reporting period for AEs and concomitant medication starts immediately following the time that written informed consent is obtained and ends 28 (+7) days after the last dose of study drug or until the initiation of subsequent anticancer therapy. For patients dose-reduced to levels -1 or -2 of AZD9150 in Arms B1, B3, or B7 who are experiencing treatment-related AEs of Grade 2 or lower, visits on Day 8 and Day 22 of each cycle (no AZD9150 dosing) may be considered optional, unless, in the Investigator's estimation, more frequent individual evaluations are appropriate.

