6.4 Recording of adverse events

6.4.1 Time period for collection of adverse events

AEs and concomitant medications will be collected and reported throughout the study. The reporting period for AEs and concomitant medication starts immediately following the time that written informed consent is obtained and ends 28 days (+7 days) after the last dose of

study drug or until the initiation of subsequent anticancer therapy. SAEs occurring in the follow-up period should be reported to AstraZeneca in the usual manner (see Section 6.5).

Safety follow-up for IM continues for all patients for 90 days (± 2 days) after the last dose of MEDI4736 or until the initiation of subsequent anticancer therapy.

SAEs will be recorded from the time of informed consent.

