Any AE occurring before the first dose of IP will be included in the data listings but will not be included in the summary tables of AEs. Summary tables will include only AEs observed following the beginning of combination dosing up to and including 28 days after last dose. One table summarising the incidence of AE occurring from the beginning of monotherapy up to the beginning of combination therapy will be generated.

Any AE occurring within the defined 28-day follow-up period after discontinuation of IP will be included in the AE summaries. AEs occurring after the 28-day follow-up period after discontinuation of IP will be listed separately but not included in the summaries.

Haematology, clinical chemistry, vital signs, and ECG data will be listed individually by patient and suitably summarised. For all laboratory variables, which are included in the current version of CTCAE, the CTCAE grade will be calculated. Summary statistics of mean, median, standard deviation, minimum, maximum, and number of observations will be used.

Details of any deaths will be listed for all patients.

For urinalysis parameters, any qualitative assessments will be summarised for all patients using the number of patients with results of negative, trace, or positive.

Graphical presentations of safety data will be presented as is deemed appropriate. This may include, but is not restricted to, presentation of parameters against time, concentration or shift plots. Appropriate scatter plots will also be considered to investigate trends in parameters compared with baseline.

Pharmacokinetics

Plasma concentrations for each of the drug substances AZD9150, AZD5069, tremelimumab, and MEDI4736 measured within each of the combination groups with any associated metabolites will be summarised by nominal sample time.

The following summary statistics will be presented for plasma concentrations at each time point and for the following PK parameters including, AUC, AUC₍₀₋₂₄₎, AUC₍₀₋₄₈₎, AUC_(0-t), AUC_(ss), C_{max}, C_{ss max}, C_{trough}, and C_{ss min}:

- The geometric mean (calculated as $\exp[\mu]$, where μ is the sample mean of the data on a logarithmic scale)
- Coefficient of variation (calculated as $100 \sqrt{[\exp(s^2)-1]}$, where s is the standard deviation of the data on a log-scale)
- Gmean \pm standard deviation (calculated as $\exp[\mu \pm s]$)
- Arithmetic mean calculated using untransformed data
- Standard deviation calculated using untransformed data
- Minimum
- Maximum

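### SAP 11.3 adverse event summary windows do not match the period in which adverse events are collected, and the change from protocol 8.10 is not recorded

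*SAP*

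**What the plan says.** **Collection.** Under protocol Section 6.4.1 and the Table 5 footnote in Section 5.2, AE reporting starts at consent and "ends 28 (+7) days after the last dose of study drug or until the initiation of subsequent anticancer therapy". Section 6.4.1 adds that SAEs in the follow-up period are reported as usual. It also describes a 90-day follow-up after MEDI4736, but for IM, which the abbreviation list defines as immunogenicity. SAP Section 6.2 puts the follow-up visit at 28 (+7) days after the last dose.

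**Protocol summary rule.** Section 8.10: "Summary tables will include only AEs observed following the beginning of combination dosing up to and including 28 days after last dose". Later AEs are listed only. One separate table covers the period from the start of monotherapy to the start of combination dosing.

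**SAP summary rule.** Section 11.3 says that "only the following TEAEs or treatment-emergent SAEs will be summarized in the summary tables" and then gives three windows:

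- monotherapy arms, AEs: "TEAEs from the first dose date of the study drug up to 30 days after the last dose date";
- monotherapy arms, SAEs: "treatment-emergent SAEs from the first dose date of the study drug up to 35 days after the last dose date";
- combination arms, AEs and SAEs alike: "from the first dose date of the study drug up to 90 days after the last dose date of MEDI4736".

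The opening paragraph of Section 11.3 says something different: every AE after the first dose is summarised, and all AEs are listed. SAP Section 13 records changes only to the PK, PD and Efficacy set definitions.

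**The concern.** A summary window should lie inside the period in which events are looked for, and it should follow exposure to every component of the regimen. The combination-arm window does neither. It runs past the end of routine AE reporting, and it is tied to one of the two or three drugs the patient receives. The monotherapy windows raise a smaller problem, because AEs and SAEs have different end points.

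Safety is a primary endpoint of Part A and a stated objective of Part B. Tables built as written would show incidences over windows that differ by arm type and are only partly observed. A reader of the tables could not tell that few events late in the window may mean few were sought. The departure from protocol 8.10 is also undeclared.

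**Working it through.** The plan states no figure to reproduce, so the check is day arithmetic.

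**Inputs.** Let day 0 be the last MEDI4736 dose, which falls on Day 1 of a 28-day cycle (protocol 7.2.3). Let L be the number of days from then to the last dose of any study drug. The SAP combination window ends on day 90. Collection ends between day L + 28 and day L + 35.

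**1. Window days without routine collection of non-serious AEs.** This is 90 − (L + 35) to 90 − (L + 28), that is, 55 − L to 62 − L.

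| Last AZD dose | L | Collection ends (day) | Days not covered |
|---|---|---|---|
| Same day as MEDI4736 | 0 | 28 to 35 | 55 to 62 |
| AZD9150 every 2 weeks, Day 15 (B8) | 14 | 42 to 49 | 41 to 48 |
| AZD9150 weekly, Day 22 | 21 | 49 to 56 | 34 to 41 |
| AZD5069, Day 28 | 27 | 55 to 62 | 28 to 35 |

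The range is 28 to 62 days, or 31% to 69% of the window (28/90 and 62/90). It assumes that no subsequent anticancer therapy starts before day L + 28. An earlier start ends collection sooner and lengthens the gap, because the SAP window has no such cut-off.

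**2. AZD9150 or AZD5069 continuing after MEDI4736 stops.**

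- Collected AEs begin to fall outside the window once L + 35 > 90, so L > 55 (or L > 62 with the 28-day end).
- On-treatment AEs fall outside once L > 90, and L − 90 on-treatment days are then excluded.
- Illustrations with assumed values: L = 120 excludes 30 days, and L = 180 excludes 90.

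**3. Patients who never receive MEDI4736.** MEDI4736 starts on Cycle 1 Day 1, after a 7-day lead-in on AZD9150 or AZD5069 alone. The Safety set (SAP Section 5) needs only one dose of AZD9150, AZD5069 or MEDI4736. A combination-arm patient who stops in the lead-in is therefore in the Safety set with no last MEDI4736 date, and the window has no end.

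**4. Monotherapy arms.** The AE window runs 30 − 28 = 2 days past the earliest end of collection and stops 35 − 30 = 5 days short of the latest. The SAE window equals 28 + 7 = 35. An SAE on days 31 to 35 enters the SAE row but not the AE row of the same overall summary. B5 and B6 each plan 12 evaluable patients, so one patient is 1/12, about 8 percentage points. SAP 11.3 does not say which window applies to a B5 or B6 patient who adds MEDI4736.

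**5. Start point.** The SAP starts at the first dose of study drug, which includes the lead-in. Protocol 8.10 starts at combination dosing and keeps the lead-in in its own table. SAP 11.3 also plans that lead-in table, so lead-in AEs would appear twice. Taken literally, 8.10 gives B5 and B6 no start.

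**The case against.** **Ninety days is not arbitrary.** Protocol 6.12 builds 90 days of follow-up into the primary data cut-off, and patients who stop MEDI4736 are sampled at 90 days. This stands as an explanation of the figure. It does not show that AEs are collected for that long, because the 90-day follow-up in 6.4.1 is for immunogenicity and the same section ends AE reporting at 28 (+7) days.

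**Something is still captured late.** A reader might infer that nothing is recorded after day 35. The documents do not support that. SAEs in follow-up are reported as usual, Section 6.4.2 asks for later SAEs judged possibly related, Section 4.2.3 sets follow-up at a minimum of 28 (+7) days, and Section 8.10 expects some later AEs to list. The gap concerns routine collection of non-serious AEs.

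**Losing on-treatment AEs is hypothetical.** No section sets out continuing AZD9150 or AZD5069 alone after MEDI4736, and the toxicity tables in Section 6.9.1 speak of discontinuing study drug treatment. Nothing forbids it either, and the documents give separate follow-up to patients who discontinue MEDI4736. The loss is therefore possible, of unknown frequency, and confined to summary tables because all AEs are listed.

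**Little inference depends on it.** Dose-limiting toxicity is assessed over the first 35 days, so the dose determination in Part A is not touched. Safety is descriptive with no testing. Both points stand. They limit the consequence to the accuracy and readability of the AE tables.

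**Conclusion.** The mismatch is real and should be corrected before the tables are programmed. Its size is bounded as follows.

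- **Combination arms:** 28 to 62 of the 90 post-MEDI4736 days lack routine collection of non-serious AEs, if the last AZD9150 or AZD5069 dose falls in the final MEDI4736 cycle. The figure of 55 to 62 days applies only when both drugs stop on the same day and should not be read as general.
- **Anchor:** the window is undefined for a combination-arm patient who stops in the lead-in. The exclusion of on-treatment AEs is conditional on more than 90 days of further AZD9150 or AZD5069. The number of patients in either group is not in the documents.
- **AEs against SAEs:** the inconsistency is limited to B5 and B6 and to days 31 to 35. The combination arms use the same 90 days for both.

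A reader might go further and conclude that on-treatment events will be lost from the study record, or that the Part A dose conclusions are unsafe. The documents support neither.

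**What to change.** For the main AE and SAE tables, use one window in all arms, ending 28 (+7) days after the last dose of any study drug or at the start of subsequent anticancer therapy, whichever comes first. Say how the program applies the +7: a 35-day cut covers everything routinely collected, while a 28-day cut is what protocol 8.10 names. This removes the uncovered stretch and the dependence on a MEDI4736 date, and it makes AEs and SAEs agree.

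Then:

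- show later reported events, for example SAEs to 90 days after the last MEDI4736 dose, in a supplementary table or listing that states what was collected in that period;
- reconcile the start point with protocol 8.10, including where lead-in AEs are counted and what start applies to B5 and B6;
- say how events are assigned for B5 and B6 patients who add MEDI4736;
- align the opening paragraph of SAP 11.3 with the window rule, and delete the bracketed drafting note left in it;
- record the change in SAP Section 13.

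The cost is SAP wording, the treatment-emergent flag and one extra output. The drawback is that late events, including immune-related ones, move out of the main tables, which is why the supplementary display is needed. No patient procedure changes.
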